#### 4.2.4.3 Primary Analysis of Secondary Endpoint

DCR at study week 15 is presented with a two-sided 90% CI using the Clopper-Pearson (exact probability) method. The main analysis of DCR is based on the Response Evaluable population.

#### 4.2.5 Secondary Endpoint: Duration of Response

Duration of Response (DoR) is a secondary endpoint.

##### 4.2.5.1 Definition

DoR is defined as the time from the date of first documented objective response (which is subsequently confirmed) until date of first documented disease progression or death (by any cause in the absence of disease progression).

##### 4.2.5.2 Derivations

$$\text{DoR (Months)} = \frac{(\text{Date of PFS event or censoring-date of first OR that is subsequently confirmed}) + 1}{(\frac{365.25}{12})}$$

where PFS event is progression or death.

The end of response should coincide with the date of progression or death from any cause used for the PFS endpoint. The time of the initial response is defined as the latest of the dates contributing towards the first visit response of CR or PR (which was subsequently confirmed). If a participant does not progress following a response, then their DoR is censored on the PFS censoring date. Only participants who have achieved OR (confirmed CR or confirmed PR) are evaluated and summarised for DoR.

##### 4.2.5.3 Handling of dropouts and missing data

Handling of missing TL data is described in Appendix A (Section [7.1](#)).

#### **4.2.5.4 Primary Analysis of Secondary Endpoint**

Only participants who have achieved objective response (CR or PR) are included in the summaries of DoR. If participant numbers allow (i.e., more than 5 participants are evaluated for DoR), Kaplan-Meier plots of DoR are presented. The median DoR and two-sided 90% CI are estimated using the Kaplan-Meier method. The percentage of participants remaining in response at 3, 6, 9 and 12 months, calculated using the Kaplan-Meier technique, are also presented. Swimmer plots that clearly show the profile of each participant who respond are also produced.

#### **4.2.5.5 Sensitivity Analyses of the Secondary Endpoint**

Sensitivity analysis is NA.

#### **4.2.5.6 Subgroup Analyses**

Subgroup analyses is defined in section [4.2.2.6](#)

### **4.2.6 Secondary Endpoint: Progression Free Survival**

Progression Free Survival (PFS) is a secondary endpoint.

#### **4.2.6.1 Definition**

The PFS is defined as the time from first dose of IP until the date of first documented disease progression or death (by any cause in the absence of progression), regardless of whether the participant withdraws from study intervention or receives another anti-cancer therapy prior to progression.

#### **4.2.6.2 Derivations**

$$\text{PFS (Months)} = \frac{(\text{Date of PFS event or censoring}-\text{date of first dose of IP})+1}{\left(\frac{365.25}{12}\right)}$$

where PFS event is progression or death.

Participants who have not progressed or died at the time of analysis are censored at the time of the latest date of assessment from their last evaluable disease assessment. However, if the participant progresses or dies immediately after two or more consecutive missed visits, the participant is censored at the time of the latest evaluable disease assessment prior to the two missed visits. Note: a NE visit is not considered as a missed visit.

Given the scheduled visit assessment scheme (i.e., first visit at week six, then nine-weekly for till 52 weeks then twelve-weekly thereafter) the definition of 2 missed visits changes.

If the previous RECIST v1.1 assessment is less than study day 288 (i.e. study week 42) and greater than study day 99 (study week 15), then two missed visits equates to 20 weeks since

the previous RECIST v1.1 assessment, allowing for early and late visits (i.e.  $2 \times 9$  weeks + 1 week for an early assessment + 1 week for a late assessment = 20 weeks).

If the previous RECIST visit is after the visit assessment at study week 6 or study week 15, then two missed visits equate to:

- 15 weeks (105 days), if study week 6 (5 weeks after 1st IP dose) and study week 15 (14 weeks after 1st IP dose) are the two consecutive visits missed [ $(1 \times 5 \text{ weeks}) + (1 \times 9 \text{ weeks}) + 1 \text{ week for late assessment}$ ].
- 19 weeks (133 days), if study week 15 (14 weeks after 1st IP dose) and week 24 (23 weeks after 1st IP dose) are the two consecutive visits missed [ $(1 \times 9 \text{ weeks}) + (1 \times 9 \text{ weeks}) + 1 \text{ week for late assessment}$ ].

If the two missed visits occur over the period when the scheduled frequency of RECIST v1.1 assessments changes from nine-weekly to twelve-weekly this equates to 23 weeks (i.e. take the average of 9 and 12 weeks which gives 10.5 weeks and then apply same rationale, hence  $2 \times 10.5 \text{ weeks} + 1 \text{ week for an early assessment} + 1 \text{ week for a late assessment} = 23 \text{ weeks}$ ). The time period for the previous RECIST v1.1 assessment is from study days 288 to 351 (i.e., study week 42 to study week 51).

From study day 351 (study week 51 onwards [when the scheduling changes to twelve-weekly assessments]), two missed visits equate to 26 weeks (i.e.  $2 \times 12 \text{ weeks} + 1 \text{ week for an early assessment} + 1 \text{ week for a late assessment} = 26 \text{ weeks}$ ). This is also summarised in the [Table 8](#) below.

Where study day, is the number of days on the study, in which Cycle 1 Day 1 is taken as study day 1.

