The DCR at 15 weeks is defined as the percentage of participants who have a BoR of CR or PR in the first 16 weeks (to allow for late assessment within the assessment window) or who have SD for at least 14 weeks after the start of treatment (to allow for early assessment within the assessment window). The DCR and its 90% CIs (Clopper Pearson method; Clopper et al, 1934) will be summarised.

Percentage Change in Tumour Size

The percentage change in TL tumour size from baseline will be summarised using descriptive statistics by timepoint. Best percentage change will also be summarised.

Waterfall plots showing the percentage change at 15 weeks and the best percentage change from baseline in sum of the diameters of TLs will be produced. Spider plots showing the percentage change from baseline in tumour size for each participant over time will be produced.

Progression-free Survival

The PFS is defined as the time from the start of study intervention until the date of objective disease progression or death (by any cause in the absence of progression), regardless of whether the participant withdraws from study intervention or receives another anti-cancer therapy prior to progression. Participants who have not progressed or died at the time of analysis will be censored at the time of the latest date of assessment from their last evaluable RECIST assessment.

The PFS time will always be derived, based on scan/assessment dates, not visit dates.

The RECIST assessments/scans contributing towards a particular visit may be performed on different dates. The following rules will be applied:

- Date of progression will be determined, based on the earliest of the dates of the component that triggered the progression.
- When censoring participants for PFS, the participant will be censored at the latest of the dates contributing to a particular overall visit assessment.

Progression-free survival will be summarised descriptively, and Kaplan-Meier plots will be provided.

Overall Survival

Overall survival is defined as the time from the start of treatment until death due to any cause. Any participant not known to have died at the time of analysis will be censored based on the last recorded date on which the participant was known to be alive.

Overall survival will be summarised descriptively, and Kaplan-Meier plots will be provided.

Change in ctDNA

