## 2 CHANGES TO PROTOCOL PLANNED ANALYSES

The following changes have been applied to this version of the SAP and are pending update in the protocol:

- The end of study definition in CSP section 4.4 will change from last IP dose to first IP dose, “The end of study is defined as 18 months after the last enrolled participant received his/her first dose of study IP or when the sponsor stops the study, whichever occurs first.”

- The definition of screen failures, in CSP section 5.4, will change in the protocol. Screen failures are patients who have been enrolled but failed to meet the study inclusion/exclusion criteria.
- At the completion of Substudy 1 Part A, all appropriate data will be presented to answer the primary analysis endpoint which will evaluate Dose Limiting Toxicities (DLTs) and determine the MTD. This deviates from the protocol which suggests all data will be presented. Presenting data only applicable to the primary endpoint of Part A, ensures the question is sufficiently answered in a timely manner, and prevents other data not needed for this endpoint being analyzed too early and too often during the study which could have a detrimental affect trial integrity.

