**Table 8: Two missed visits rule for PFS for schedule changes**

Scheduled Assessment	Previous RECIST assessment	Two missed RECIST visits window
5 weeks up to study week 6 then Q9 till study week 52	No evaluable RECIST visits or no baseline RECIST scan	$(1 \times 5 \text{ weeks}) + (1 \times 9 \text{ weeks}) + 1 \text{ week} = 15 \text{ weeks (105 days)}$
5 weeks up to study week 6 then Q9 till study week 52	Baseline	$(1 \times 5 \text{ weeks}) + (1 \times 9 \text{ weeks}) + 1 \text{ week} = 15 \text{ weeks (105 days)}$
5 weeks up to study week 6 then Q9 till study week 52	Study day 36 (Study week 6)	$2 \times 9 \text{ weeks} + 1 \text{ week} = 19 \text{ weeks (133 days)}$
Q9W till study week 52	>Study day 99– Study day 288 (From study week 15 up to study week 42)	$2 \times 9 \text{ weeks} + 2 \text{ weeks} = 20 \text{ weeks (140 days)}$
	>Study day 288 – Study day 351 (Study week 42 – Study week 51) (change period from Q9W to Q12W)	$2 \times [(9 \text{ weeks} + 12 \text{ weeks})/2] + 2 \text{ weeks} = 23 \text{ weeks (161 days)}$
Q12W thereafter	>Study Day 351 onwards	$2 \times 12 \text{ weeks} + 2 \text{ weeks}$

RECIST = Response Evaluation Criteria in Solid Tumours v1.1;

If the participant has no evaluable disease assessments post-baseline or does not have baseline tumour assessment data, they are censored at Day 1 unless they die within two visits of first IP dose (14 weeks plus 1 week allowing for a late assessment within the visit window) then the death date qualifies as a PFS event.

A summary of censoring rules and the date of progressive disease/death or censoring are given in [Table 9](#). Note that censoring overrides event in certain specified cases and the table below does not indicate the order for programming.

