**Table 9: Summary of Censoring Rules for PFS**

Situation	Date of progressive disease /Death or Censoring	PFS Outcome
Documented Progressive Disease or death in the absence of progression	Date of earliest documentation of progressive disease or date of death in the absence of progression	Event
Either no tumour assessment at baseline or no evaluable assessments post-baseline AND death prior to second scheduled post-baseline disease assessment	Date of death	Event
Either no tumour assessment at baseline or no evaluable assessments post-baseline AND no death prior to second scheduled post-baseline disease assessment	Date of first dose (Day 1)	Censored
Progressive disease or death (in the absence of progression) immediately after $\geq 2$ consecutive missed disease assessments as per the protocol specified assessment schedule	Last evaluable progression-free disease assessment prior to missed assessments (if available). Otherwise, the date of censoring is Date of first dose (Day 1)	Censored
On-going with neither progressive disease nor death at the time of analysis or lost to follow-up or withdrawn consent	Date of last evaluable disease assessment	Censored

PFS = progression-free survival

The PFS time is always derived based on scan/assessment dates, and not on visit dates.

RECIST v1.1 assessments/scans contributing towards a particular visit may be performed on different dates. The following rules are applied:

- The date of progression is determined based on the earliest of the dates of the component that triggered the progression.
- When censoring a participant for PFS the participant is censored at the latest of the dates contributing to a particular overall visit assessment.

Note: for TLs only the latest scan date is recorded out of all scans performed at that assessment for the TLs and similarly for NTLs only the latest scan date is recorded out of all scans performed at that assessment for the NTLs.

The number of participants alive and progression free at 3, 6, 9 and 12 months (PFS-3, PFS-6, PFS-9, and PFS-12) is defined as the Kaplan-Meier estimate of PFS at 3, 6, 9 and 12 months.

‘Potential’ duration of follow-up for PFS is applicable only for PFS censored participants and is defined as follows:

$$\text{Potential duration of follow up for PFS (Months)} = \frac{\text{(Date of PFS censoring-date of first dose of IP)} + 1}{\left(\frac{365.25}{12}\right)}$$

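### The SAP censors PFS events that follow two missed assessments, where the protocol counts them; SAP section 2 does not list the change and no analysis by the protocol definition is planned

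*SAP*

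**What the plan says.** Protocol 9.4.3 runs PFS from the start of study intervention "until the date of objective disease progression or death (by any cause in the absence of progression"). Its only rule for who is censored is that "Participants who have not progressed or died at the time of analysis will be censored", at the last evaluable RECIST assessment. It does not mention missed visits.

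SAP 4.2.6.1 keeps the same endpoint, running "until the date of first documented disease progression or death (by any cause in the absence of progression"). SAP 4.2.6.2 then adds an exception: "if the participant progresses or dies immediately after two or more consecutive missed visits, the participant is censored". Table 8 gives the windows that define two missed visits. Table 9 sets the censoring date at the last evaluable progression-free assessment before the gap, or Day 1 if there is none. For participants with no evaluable post-baseline assessment, or no baseline assessment, the text after Table 8 says "they are censored at Day 1 unless they die within two visits of first IP dose", and puts that limit at 14 weeks plus 1. A visit assessed as not evaluable does not count as missed.

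SAP section 2 opens with "The following changes have been applied to this version of the SAP and are pending update in the protocol" and gives three items: the end-of-study definition, the screen-failure definition, and which data are presented at the end of Part A. None concerns PFS. SAP 4.2.6.4 plans one PFS analysis, on the safety analysis set, with this one censoring scheme.

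**The concern.** A documented progression or death is an event under the protocol and a censored observation under the SAP whenever it follows a long enough gap in scanning. That changes the endpoint; it does more than add technical detail. In advanced disease, people often miss scans because they are deteriorating, so censoring at the last scan before the gap is likely to be informative. It ties the PFS estimate to scan attendance.

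The rule reaches further than PFS. SAP 4.2.5.2 takes the end of DoR from the PFS event or censoring date. SAP 4.2.4.2 refers to the PFS censoring date in the duration of SD that feeds DCR at study week 15. SAP Table 1 also lists PFS among the efficacy data at the Part C interim.

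As the plan stands, the PFS estimate that the protocol defines would not be reported, and a reader who compares the protocol with SAP section 2 would not learn that it had been replaced.

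**Working it through.** **1. The SAP windows reproduce.** From the scan schedule in SAP 4.2.6.2:

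- no evaluable visit, or baseline only: 5 + 9 + 1 = 15 weeks = 105 days
- last scan at study week 6: 9 + 9 + 1 = 19 weeks = 133 days
- last scan from study week 15 to 42: 2 × 9 + 2 = 20 weeks = 140 days
- last scan from study week 42 to 51: 2 × 10.5 + 2 = 23 weeks = 161 days
- later: 2 × 12 + 2 = 26 weeks = 182 days

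**2. The same participant under each rule.**

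- Last evaluable scan on study day 36, no further scan, then death. The protocol counts an event on the date of death. Under the SAP, a death more than 133 days after that scan (after about day 36 + 133 = 169) is censored at day 36.
- No post-baseline scan, then death. The protocol counts an event on the date of death. Under the SAP, a death within 105 days is still an event; a later one is censored at Day 1.
- Alive without progression at analysis. Censored under both, so here the SAP only fills in detail.

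**3. Size of the effect.** The documents give no progression, survival or missed-scan rates for PFS, so every rate below is an assumption. Each run applies the SAP schedule and windows and compares Kaplan-Meier estimates under the two rules.

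*Mechanism A.* 20,000 participants per scenario; median latent time to progression 80 days; median survival after progression 150 days; 18-month cut-off. A stated share never has the scan that would show progression.

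| Share missed | Event to censored | Six-month PFS, protocol | Six-month PFS, SAP | Difference (points) |
|---|---|---|---|---|
| 10% | 4.7% | 28.5% | 26.6% | 1.9 |
| 20% | 9.4% | 32.9% | 29.3% | 3.6 |
| 30% | 14.4% | 36.6% | 31.1% | 5.5 |

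A separate repeat gave 4.7%, 9.7% and 14.0% switching, with differences of 28.1 − 26.3 = 1.8, 32.1 − 28.5 = 3.6 and 35.6 − 30.3 = 5.3 points. Over further runs of this mechanism the ranges were about 4–15% and 1–6 points.

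*Mechanism B.* 40 participants (one expansion), 400 replicates, 540 days of follow-up. A stated share stops scanning after 0, 1 or 2 scans. The first column gives the median time to progression, then from progression to death, in months.

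| Medians | Share stopping | Events lost of 40 | Six-month PFS, protocol | Six-month PFS, SAP | Difference (points) |
|---|---|---|---|---|---|
| 2, 4 | 10% | 1.8 | 18.1% | 15.5% | 2.6 |
| 2, 4 | 30% | 5.1 | 22.4% | 14.4% | 8.0 |
| 2, 8 | 10% | 1.6 | 18.0% | 15.2% | 2.8 |
| 2, 8 | 30% | 4.2 | 22.9% | 15.5% | 7.4 |
| 4, 4 | 10% | 2.0 | 41.3% | 39.3% | 2.0 |
| 4, 4 | 30% | 6.1 | 45.2% | 38.6% | 6.6 |
| 4, 8 | 10% | 1.6 | 40.9% | 39.3% | 1.6 |
| 4, 8 | 30% | 4.8 | 44.3% | 38.5% | 5.8 |

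The 20% scenarios fall between these. Events lost run from 1.6/40 = 4% to 6.1/40 = 15%. The typical median is the same under both rules throughout: 3.22 months in the first four rows and 5.29 in the last four.

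**4. Against sampling error.** With 40 participants and six-month PFS of 32.9%, the binomial standard error is √(0.329 × 0.671 / 40) = 0.074, about 7 points. A 3.6-point difference is about half of that.

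**The case against.** The strongest defence has four parts.

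*The rule is not hidden.* It has its own text and two tables, the SAP amendment history revises its windows, and protocol 9.4 leaves technical detail to the SAP. This stands as far as openness goes. But an exception that turns a documented death into a non-event changes the endpoint, and section 2 is where the SAP records such changes.

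*The protocol works against missed scans.* Scanning continues after treatment stops until progression (protocol 7.1). Table 14 asks for an end-of-treatment scan unless one was done in the preceding 14 days, with further scans at Day 90 and every 12 weeks. The simulations leave out these extra scans, so the true missed share could be at or below the low end of the range.

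*Some of the effect will be visible.* SAP 4.2.6.4 breaks PFS down by type of event and censoring, and OS counts all deaths on the same set. That may show how many events were censored, but it does not give the protocol-defined curve.

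*Little depends on PFS.* Protocol 10.9.1 has no hypotheses, protocol 10.9.4.1 excludes comparisons between cohorts, and SAP 3.3.7.2 sizes Part C on ORR precision. This stands and limits the importance of the point.

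A reader might also infer that the SAP contradicts itself on deaths without a scan, because Table 9 says "AND no death prior to second scheduled post-baseline disease assessment" while the text allows 15 weeks. The documents do not support that. Table 9 gives no number of weeks. Protocol Table 13 places the second assessment in days 1 to 7 of week 15, which is study days 14 × 7 + 1 = 99 to 15 × 7 = 105, so its window closes at the same 15 weeks.

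**Conclusion.** The point holds as a departure from the protocol's PFS definition that SAP section 2 omits, with no planned analysis by that definition. SAP 3.3.5 provides for sensitivity analyses only where protocol deviations may affect the primary analysis, so it does not fill the gap. On assumed missed-scan shares of 10–30%, about 4–15% of participants move from event to censored. Six-month PFS is then about 1–6 points lower under the SAP rule if single progression scans are missed, and about 2–8 points lower if participants stop scanning early.

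Two stronger readings are tempting and should not be drawn. The first is that the SAP rule flatters the drug. In every scenario run it gave the lower six-month PFS, because the protocol rule treats the unscanned gap as event-free until death. That direction is a result of these scenarios and is not guaranteed; later time points were not compared. Neither rule is free of bias, and which should be the main analysis is a matter of judgement.

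The second is that median PFS will shift. It did not in any Mechanism B scenario. Under Mechanism A it moves in some scenarios only: at 20% missed it moved with an 80-day latent median, where the curve at the day-99 scan was 0.511 under one rule and 0.484 under the other, and not with 70, 100 or 120 days. Such a shift depends on where the curve crosses 0.50 on the scan grid.

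PFS is a descriptive secondary endpoint, so no error rate or power is affected. The point is worth correcting but is not critical.

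**What to change.** - Add the missed-visit rule to SAP section 2 as a change to protocol 9.4.3, including the Day 1 fallback and the carry-over into DoR and the duration of SD.
- Add one sensitivity Kaplan-Meier analysis of PFS and DoR in which all documented progressions and deaths count as events at their dates and only participants with neither are censored. The missed-visit rule can remain the main analysis.
- Optional wording: repeat the 15-week limit in Table 9.

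This uses data already collected. The cost is a short SAP edit and one extra Kaplan-Meier output per part.

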**Table 8: Two missed visits rule for PFS for schedule changes**

Scheduled Assessment	Previous RECIST assessment	Two missed RECIST visits window
5 weeks up to study week 6 then Q9 till study week 52	No evaluable RECIST visits or no baseline RECIST scan	$(1 \times 5 \text{ weeks}) + (1 \times 9 \text{ weeks}) + 1 \text{ week} = 15 \text{ weeks (105 days)}$
5 weeks up to study week 6 then Q9 till study week 52	Baseline	$(1 \times 5 \text{ weeks}) + (1 \times 9 \text{ weeks}) + 1 \text{ week} = 15 \text{ weeks (105 days)}$
5 weeks up to study week 6 then Q9 till study week 52	Study day 36 (Study week 6)	$2 \times 9 \text{ weeks} + 1 \text{ week} = 19 \text{ weeks (133 days)}$
Q9W till study week 52	>Study day 99– Study day 288 (From study week 15 up to study week 42)	$2 \times 9 \text{ weeks} + 2 \text{ weeks} = 20 \text{ weeks (140 days)}$
	>Study day 288 – Study day 351 (Study week 42 – Study week 51) (change period from Q9W to Q12W)	$2 \times [(9 \text{ weeks} + 12 \text{ weeks})/2] + 2 \text{ weeks} = 23 \text{ weeks (161 days)}$
Q12W thereafter	>Study Day 351 onwards	$2 \times 12 \text{ weeks} + 2 \text{ weeks}$

RECIST = Response Evaluation Criteria in Solid Tumours v1.1;

If the participant has no evaluable disease assessments post-baseline or does not have baseline tumour assessment data, they are censored at Day 1 unless they die within two visits of first IP dose (14 weeks plus 1 week allowing for a late assessment within the visit window) then the death date qualifies as a PFS event.

A summary of censoring rules and the date of progressive disease/death or censoring are given in [Table 9](#). Note that censoring overrides event in certain specified cases and the table below does not indicate the order for programming.

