#### 4.2.7.2 Derivations

For visit based summaries, whenever TL tumour size data for each post-baseline assessment (note: or visit at which progression was documented if before the post-line visit) is available then this is used in the analysis. A windowing rule is applied and follows the protocol allowed visit window; therefore, any RECIST v1.1 scan performed within Study W6(D1-D7), W15(D1-D7), W24 $\pm$ 6D then Q9W $\pm$ 6D until W52, then Q12W $\pm$ 6D of the protocol scheduled visit is used for that visit.

The percentage change from baseline in TL tumour size at each post-baseline assessment is obtained for each participant taking the difference between the sum of the TLs at each post-baseline assessment and the sum of the TLs at baseline divided by the sum of the TLs at baseline times 100. For example, the percentage change from baseline in TL tumour size for the post-baseline visit at study week 15 is calculated as follows:

$$\text{Percentage change from baseline in TL tumour size} \\ = \frac{(\text{Study Week 15} - \text{Baseline})}{(\text{Baseline})} \times 100$$

For best percentage change, if it cannot be calculated due to missing data (including if the participant has no TLs at baseline), a value of +20% is imputed as the best percentage change from baseline in the following situations (otherwise best percentage change is left as missing):

- If a participant has no post-baseline assessment and has died;
- If a participant has new lesions or progression of NTLs or TLs;
- If a participant has withdrawn due to progressive disease and has no evaluable TL data before or at progressive disease.

For the outcome endpoint percentage change from baseline in TL tumour size at each post-baseline assessment i.e., Study week 15, participants who progress before study week 15 should have had a tumour assessment performed at the time of progression prior to treatment discontinuation. The tumour size from their latest progression assessment is used instead of the study week 15 assessment for these participants.

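### The two-missed-visits cut-offs for PFS in SAP Table 8 sit on the nominal W42 and W51 days, so progression found after a single missed scan can be censored as if two had been missed

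*SAP*

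**What the plan says.** SAP 4.2.6.2 censors PFS at the last evaluable scan "if the participant progresses or dies immediately after two or more consecutive missed visits". SAP Table 9 repeats the condition as two or more "consecutive missed disease assessments as per the protocol specified assessment schedule". A missed visit is not identified directly. Instead, the gap since the previous scan is compared with a limit that depends on the study day of that scan.

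- **20 weeks.** Table 8 applies this to ">Study day 99– Study day 288 (From study week 15 up to study week 42". The text applies it when the previous scan is "less than study day 288 (i.e. study week 42) and greater than study day 99 (study week 15".
- **23 weeks.** Table 8 applies this to days after 288 up to 351. The text gives the principle, "If the two missed visits occur over the period when the scheduled frequency of RECIST v1.1 assessments changes from nine-weekly to twelve-weekly", and then the range: "The time period for the previous RECIST v1.1 assessment is from study days 288 to 351".
- **26 weeks.** Table 8 applies this after day 351. The text says: "From study day 351 (study week 51 onwards [when the scheduling changes to twelve-weekly assessments]), two missed visits equate to 26 weeks".

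Protocol Table 13 allows ±6 days around each scan from W24 onward. SAP 4.2.7.2 uses that allowance for tumour size: "A windowing rule is applied and follows the protocol allowed visit window".

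**The concern.** Each limit contains one week for an early scan and one for a late scan, but the band edges contain no such allowance. After W42 the next two intervals are 9 and 12 weeks; after W51 they are 12 and 12 weeks. A scan done early, or exactly on day 288 or 351 under Table 8, falls in the preceding band and gets a limit built for shorter intervals. The next-but-one scheduled scan then lies beyond the limit although only one scan was missed.

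The text and Table 8 also conflict. Day 288 is in the 20-week band in the table and the 23-week band in the text. Day 351 is in the 23-week band in the table and in both the 23- and 26-week bands in the text. Two programmers could derive different outcomes from the same data.

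What is at stake is the loss of late progression events. SAP 4.2.5.2 ends DoR on the PFS event or censoring date, so DoR inherits the error, and SAP 4.2.5.4 reports DoR rates out to 12 months. W63 and W75 (days 435 and 519) fall within the 18 months of follow-up planned after the last participant's first dose (18 × 30.4375 = 548 days).

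**Working it through.** **Inputs.** Cycle 1 Day 1 is study day 1 (SAP 4.2.6.2), so the nominal day of week w is 7 × (w − 1) + 1. Scans from W24 are 9-weekly to W52 and then 12-weekly, each ±6 days (Protocol Table 13). The 12-weekly schedule starts at W51 (SAP 4.2.6.2), giving W63, W75 and W87.

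**1. The plan's limits reproduce.** 7 × (2 × 9 + 2) = 140 days; 7 × (2 × 10.5 + 2) = 161 days; 7 × (2 × 12 + 2) = 182 days.

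**2. Scan days.** W42: 288 (282–294). W51: 351 (345–357). W63: 435 (429–441). W75: 519 (513–525).

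**3. One missed scan under Table 8.** Each step has 13 × 13 = 169 pairs of previous and next scan days.

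| Previous scan | Limit | Next scan attended | Gap (days) | Wrongly censored |
|---|---|---|---|---|
| W42, days 282–288 | 140 | W63 | 429 − 288 = 141 to 441 − 282 = 159 | 91 of 91 |
| W42, days 289–294 | 161 | W63 | 429 − 294 = 135 to 441 − 289 = 152 | 0 of 78 |
| W51, days 345–351 | 161 | W75 | 513 − 351 = 162 to 525 − 345 = 180 | 91 of 91 |
| W51, days 352–357 | 182 | W75 | 513 − 357 = 156 to 525 − 352 = 173 | 0 of 78 |

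That is 91/169 = 54% at each of the two steps. It is 0 of 169 after W24 and W33 (largest gap 138 against 140) and after W63 (180 against 182).

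**4. The text's day ranges.** At W42, day 288 moves to 161 days, leaving days 282–287 wrong: 6 × 13 = 78 of 169. At W51 the count is 78 if day 351 takes 26 weeks and 91 if it takes 23. Reconciling table and text alone would therefore not repair early scans. The text's principle, applied by visit rather than by day, gives 0 of 169 at W42 (largest gap 159 against 161).

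**5. Cut-offs moved to days 282 and 345.** Largest one-miss gaps are 159 of 161 (W42) and 180 of 182 (W51), so there are 0 errors from W24 to W63. Smallest two-miss gaps are 177 (W24), 198 (W33), 219 (W42) and 240 (W51), all above their limits, so every in-window double miss is still caught. The earlier rows are sound as they stand: first dose to W15 is 98–104 days of 105, and W6 to W24 is 114–132 of 133. W15 to W33 is 114–132, so a day-99 scan is safe under either 133 or 140.

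**6. Sensitivity to the anchor.** If 12-weekly scans counted from W52 (W64 day 442, W76 day 526), Table 8 would still be wrong for 91 of 169 pairs per step. The moved cut-offs would leave 15 of 169 (for example 448 − 282 = 166 > 161).

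**7. Effect on the endpoints.** The first PFS event that can be lost is on day 282 + 141 = 423, or 423/30.4375 = 13.9 months. DoR in months is (end day − response day + 1)/30.4375:

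- Response at W15 (days 99–105), progression at W63: true DoR 325/30.4375 to 343/30.4375 = 10.7–11.3. Censored at W42: 178/30.4375 to 190/30.4375 = 5.8–6.2.
- Response at W33 (days 219–231), progression at W75: true DoR 283/30.4375 to 307/30.4375 = 9.3–10.1. Censored at W51: 115/30.4375 to 133/30.4375 = 3.8–4.4.

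**8. Numbers exposed.** The documents give no attendance rates. Assume 5–15% of participants reach W42 and 5–10% of those miss exactly one scan at a step. Exposed per step = n × (0.05 to 0.15) × (0.05 to 0.10) × 91/169: 0.05–0.32 for n = 40 (a Part C expansion), 0.01–0.08 for n = 10 (a Part B tumour-by-dose group), and 0.01–0.07 for n = 9 (a Part A cohort). These figures do not yet require progression at the next scan.

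**The case against.** The arithmetic is not in dispute; the case on the other side concerns weight and scope.

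- **Impact is very small.** PFS and DoR are secondary and descriptive, and no cohorts are compared. The Part C interim is triggered by the 20th participant's opportunity for two on-treatment scans, so it is barely touched. This stands.
- **DoR counts responders only.** Multiplying the Part C exposure by an assumed ORR of 5–20% gives about 0.003–0.065 participants per step. That shrinks the number, although it assumes responders are no more likely than others to be progression-free at W42. The DoR examples are also selected: a W6 responder progressing at W63 has 12.7–13.3 months, so no event before 12 months is lost. This stands as a limit on the effect.
- **The SAP does allow for the window.** True of the limits, but not of the band edges. The on-time failures (13 of the 91 pairs) come from which band owns the nominal day, not from the window.
- **The governing rule is already right.** Read by study week, the text would give W42 23 weeks and W51 26 weeks, with no errors. But the SAP also prints explicit day ranges and derives PFS from scan dates, and a program would follow those.
- **Fixed day cut-offs remain brittle outside the window.** A scan on day 281 is 148–160 days from W63 against 140. Assigning the limit by visit would cover that case. This is fair, but it does not affect in-window scans.
- **The 54% is conditional** on evenly spread dates, exactly one miss and the next scan being attended as scheduled. Agreed.

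**Conclusion.** The rule is wrong as written. Under Table 8, every early or on-time W42 or W51 scan followed by one missed scan leads to censoring when progression is first found at the next scheduled scan, contrary to the two-or-more condition in SAP 4.2.6.2 and Table 9. Scans 1–6 days late are handled correctly. Progression on an unscheduled scan, or death, within the 140- or 161-day limit still counts as an event. This result needs only the protocol windows and the W51 anchor, and a W52 anchor does not rescue Table 8.

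The practical effect is small: well under one participant per reported cohort under the assumed attendance rates. PFS-3, PFS-6 and PFS-9 are unaffected, and PFS-12 only loses affected participants from its risk set. The late DoR rates are the main exposure. Events lost before 12 months push the 12-month rate upward, among the few participants with durable responses.

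**What to change.** In both the text of SAP 4.2.6.2 and Table 8:

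- Apply 20 weeks to a previous scan after day 99 and up to day 281, 23 weeks to days 282–344, and 26 weeks from day 345.
- Leave the 15-week and 19-week rows and the lower bound at day 99 unchanged.
- State that 12-weekly scans count from W51 (W63, W75). The absence of single-miss errors depends on this sentence.

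Separately, align Appendix A, which places the first scan 6 weeks after first dose, with the day-36 and day-99 anchors in 4.2.6.2, and check both against Protocol Table 13.

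The cost is two constants and one anchor sentence in the SAP text, Table 8 and the program, plus one sentence in Appendix A. No data collection changes.
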